## **LIST OF ABBREVIATIONS**

AE	Adverse Event
ALT	Alanine aminotransferase
AST	Aspartate aminotransferase
ATS	All Treated Subjects
AUC(0-τ)	Area under the concentration-time curve over the dosing
	interval
β-hCG	Beta-human chorionic gonadotropin
BMI	Body mass index
CBC	Complete blood count
CL/F	Apparent clearance following oral dosing
Cmax	Maximum observed concentration
Сτ	Concentration at the end of the dosing interval
CPK	Creatine phosphokinase
CRF	Case Report Form
CTCAE	Common Terminology Criteria for Adverse Events
DSMB	Data Safety Monitoring Board
ECG	Electrocardiogram
EW	Early Withdrawal
FDA	Food and Drug Administration
FU	Follow-Up
GCP	Good Clinical Practice
GCSP	Global Clinical Safety and Pharmacovigilance
GSK	GlaxoSmithKline
HIV	Human Immunodeficiency Virus
h/hr	Hour(s)
IB	Investigator's Brochure
ICH	International Conference on Harmonization of Technical
	Requirements for Registration of Pharmaceuticals for
	Human Use
IEC	Independent Ethics Committee
IND	Investigational New Drug
IRB	Institutional Review Board
ITP	Immune (idiopathic) thrombocytopenic purpura
IU	International Unit
IV	Intravenous
Kg	Kilogram
L	Liter
Ln	Naperian (natural) logarithm
μg	Microgram
μL	Microliter
M	Month
MedDRA	Medical Dictionary for Regulatory Activities
Mg	Milligrams

mL	Milliliter
MSDS	Material Safety Data Sheet
PfOS	Powder for Oral Suspension
PGx	Pharmacogenetics
PK	Pharmacokinetic
QC	Quality control
RBC	Red blood cells
RNA	Ribonucleic Acid
SAE	Serious adverse event(s)
SOC	System Organ Class
SPM	Study Procedures Manual
tmax	Time of occurrence of Cmax
ULN	Upper limit of normal
WBC	White blood cells
WHO	World Health Organization
W (or) WK	Week

## PROTOCOL SUMMARY

#### Rationale

Study TRA117366 is an extension study for pediatric chronic ITP patients who have previously been enrolled in the TRA115450/PETIT2 study and obtain clinical benefit from treatment with eltrombopag.

## Objective(s)

• To provide continued treatment to patients who have completed the TRA115450 study and to describe the safety and tolerability of eltrombopag when administered to pediatric subjects with previously treated chronic ITP.

## **Study Design**

This is an open-label Phase III extension study to evaluate the long-term safety of eltrombopag in pediatric patients with chronic ITP who previously participated in study TRA115450. This study will allow dosing of eltrombopag at an individualized dose for each subject based upon platelet count. The starting dose will be based on the subject's dose at the end of the TRA115450 study, unless a dose adjustment is warranted due to platelet count. The maximum dose will be 75 mg daily.

[figure not shown]
Maximum twelve (n = 12) patients will be enrolled into the study. Subjects may remain on treatment in this study until at least one of the following criteria is met: the subject reaches 18 years of age or eltrombopag receives local regulatory approval for the treatment of pediatric chronic ITP.

[figure not shown]
## **Study Assessments**

The primary endpoint is the assessment of long-term safety. Safety assessments will include clinical laboratory tests, ocular examinations, and adverse event reporting.

## 1. INTRODUCTION

## 1.1. Background

## 1.2. Study Rationale

Study TRA117366 will be conducted to evaluate the long-term safety of eltrombopag in pediatric chronic ITP population. This study will allow dosing of eltrombopag at an individualized dose for each subject based upon platelet counts.

## 2. OBJECTIVE(S) AND ENDPOINTS

Objective	Endpoint				
To provide continued treatment to patients who have completed the TRA115450 study and to describe the safety and tolerability of eltrombopag when administered to pediatric subjects with previously treated chronic ITP.	Safety parameters include clinical laboratory assessments, and frequency of all adverse events, categorized using Common Terminology Criteria for Adverse Events (CTCAE) toxicity grades.				

#### 3. STUDY DESIGN

This is a Phase III study in which a screening period will be followed by a single arm treatment period and a follow-up period:

- A screening period of up to 28 days prior to Day 1 of treatment in this study
- Open-label, single arm, dose-adjustment, long-term treatment period, in which subjects may continue treatment until at least one of the following criteria are met:
  - Subject reaches 18 years of age: Subject will be considered to have completed the study, and will be discontinued from study treatment within 3 months of his/her 18th birthday.
  - Eltrombopag receives local regulatory approval for pediatric chronic ITP.
- Follow-up period. All subjects must complete the 4-week follow-up period, as described below, as part of their participation in this study:
  - Subjects who elect not to continue treatment with eltrombopag (i.e., non-study treatment) after completion of the study treatment period, will have weekly follow-up visits for 4 weeks after the last dose of study treatment.
  - Subjects who continue treatment with eltrombopag (i.e., non-study treatment) after completion of the study treatment periods will have a follow-up visit 4 weeks after the last dose of study treatment.

Maximum twelve (n = 12) subjects will be enrolled in the study.

The term 'study treatment' is used throughout the protocol to describe the product under evaluation in this protocol.

Protocol waivers or exemptions are not allowed with the exception of immediate safety concerns. Therefore, adherence to the study design requirements, including those specified in the Time and Events Table, are essential and required for study conduct

Supplementary study conduct information not mandated to be present in this protocol is provided in the accompanying Study Procedures Manual (SPM). The SPM will provide the site personnel with administrative and detailed technical information that does not impact subject safety.

#### SUBJECT SELECTION AND DISCONTINUATION/ 4. **COMPLETION CRITERIA**

CONFIDENTIAL

#### 4.1. **Subject Selection Criteria**

#### 4.1.1. **Number of Subjects**

Up to twelve (n = 12) subjects will be enrolled.

#### 4.1.2. Inclusion Criteria

Specific information regarding warnings, precautions, contraindications, adverse events, and other pertinent information on the GSK investigational product that may impact subject eligibility is provided in the IB

Deviations from inclusion criteria are not allowed because they can potentially jeopardize the scientific integrity of the study, regulatory acceptability or subject safety. Therefore, adherence to the criteria as specified in the protocol is essential.

Subjects eligible for enrolment in the study must meet all of the following criteria:

- Written informed consent must be obtained from the subject's guardian and accompanying informed assent from the subject (for children over 6 years old).
- 2. Subjects must be between 1 year and <18 years of age at Day 1.
- 3. Subjects must have enrolled in TRA115450/PETIT2 study.
- Subjects must have completed Part 1 and Part 2 of TRA115450/PETIT2 study.
- Female subjects of child-bearing potential (after menarche) must:
  - have a negative pregnancy test within 24 hours of first dose of study treatment,
  - agree and be able to provide a blood or urine specimen for pregnancy testing during the study,
  - agree to use effective contraception, as defined in Section 7.2.3, during the study and for 28 days following the last dose of study treatment, and
  - not be lactating.
- Male subjects with a female partner of childbearing potential must agree to use effective contraception as described in Section 7.2.3 from 2 weeks prior to administration of the first dose of study treatment until 3 months after the last dose of study treatment.

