#### Table 3 Time and Events Table (Continued)

W: week; FU: follow-up; M: month

Note: If the subject continues on a stable dose of eltrombopag for 3 consecutive weeks, also if at the day 1 patient received stable dose in TRA115450 for at least 3 consecutive weeks (without changes in concomitant ITP therapy), assessments may be scheduled every 4 weeks ( $\pm 7$  days of nominal visit day) rather than weekly. If the subject continues on a stable dose of eltrombopag for 3 consecutive monthly visits (without changes in concomitant ITP therapy), including any consecutive monthly visits in TRA115450 prior to coming into this study, assessments frequency may be further reduced and may be scheduled every 6 weeks ( $\pm 7$  days of nominal visit day). If the dose of eltrombopag is not stable, weekly visits ( $\pm 3$  days of nominal visit day) will be required.

- 1. Screening visit may occur on the same day as the Day 1 visit.
- 2. All subjects will attend the End of Treatment visit on the day of or within 3 days after the last dose of study treatment.
- 3. Subjects who continue on treatment with eltrombopag (i.e., non-study treatment) will not be required to attend the Week 1, 2 and 3 Follow-up visits.
- **4.** Physical Exam to be performed at screening.
- 5. For female subjects of child-bearing potential, a negative pregnancy test (urine or blood sample) MUST be obtained within 24 hours prior to the first dose. Tests to confirm that female subjects of childbearing potential are not pregnant will be conducted at least once every 8 weeks while receiving study treatment and after 4 weeks following completion or discontinuation of study treatment.
- **6.** CBC parameters: platelet count, hemoglobin, and WBC, .
- 7. Peripheral blood smear to be performed on Day 1 and at least once every 6 weeks, regardless of the visit schedule (weekly, 4-weekly or 6-weekly).
- **8.** Clinical Chemistry: Alkaline phosphatase, AST, ALT, total bilirubin, and direct bilirubin.
- 9. If clinical chemistry at follow-up week 1 is normal, no clinical chemistry will be measured at follow-up weeks 2, 3 and 4.
- 10. An age-appropriate standard of care exam will be performed to assess the presence of cataracts every 12 months while in the study treatment period.

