#### 7.2.3.1. Pregnancy Testing and Prevention

A screening pregnancy test is mandatory for all female subjects of childbearing potential, as defined below, but in no event longer than 24 hours prior to the first administration of study treatment. Unless a serum pregnancy test is required by the medical institution, a urine pregnancy test is sufficient. If the screening pregnancy test cannot be performed within 24 hours prior to the first administration of study treatment, a urine pregnancy test must be performed and results must be negative on Day 1 prior to dosing with eltrombopag. The results of this test must be negative. Thereafter, the pregnancy test will be repeated at least once every 8 weeks while receiving study treatment or more frequently if clinically indicated or required per local regulation (refer to Table 3 Time and Events Table).

The need for a screening pregnancy test depends on whether a female subject is of childbearing potential or non-childbearing potential.

A female of non-childbearing potential (i.e., physiologically incapable of becoming pregnant) is defined as a pre-menarche female or any female (after menarche) who has had a hysterectomy, bilateral oophorectomy (ovariectomy) or bilateral tubal ligation, or is post-menopausal.

**A female of child-bearing potential** is defined as any female who does not meet the criteria of non-childbearing potential as described in the previous paragraph.

If a female subject is of childbearing potential, she must have a urine or serum  $\beta$ -hCG pregnancy test performed within 24 hours prior to the first dose of study treatment. Female subjects with positive pregnancy test result must be excluded from the study. Subjects with negative pregnancy test result must agree to use an effective contraception method as described below during the study until 28 days following the last dose of study treatment.

Male subjects with a female partner of childbearing potential must agree to use one of GSK acceptable effective contraception during the study until 28 days following the last dose of study

GSK acceptable contraceptive methods, when used consistently and in accordance with both the product label and the instructions of the physician, are as follow:

- An intrauterine device with a documented failure rate of less than 1% per year.
- Vasectomized partner who is sterile prior to the female subject's entry and is the sole sexual partner for that female.

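### Protocol Sections 4.1.2 and 7.2.3.1 give inconsistent contraception periods for the same male subjects, with end points about 63 days apart

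*Protocol*

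**What the plan says.** Protocol Section 4.1.2 (Inclusion Criteria) contains this entry condition: "Male subjects with a female partner of childbearing potential must agree to use effective contraception as described in Section 7.2.3". It sets the period as running from 2 weeks before the first dose "until 3 months after the last dose of study treatment". The same section says that deviations from inclusion criteria are not allowed.

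Protocol Section 7.2.3.1 (Pregnancy Testing and Prevention) opens its rule for the same group with "Male subjects with a female partner of childbearing potential must agree to use one of GSK acceptable effective contraception" and sets a different period. The full obligation reads that they "must agree to use one of GSK acceptable effective contraception during the study until 28 days following the last dose of study". The sentence breaks off there in the available text, but the 28-day figure is legible.

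Section 7.2.3.1 then lists acceptable methods. One of them, complete abstinence, carries its own period: from 14 days before the first dose to at least 28 days after the last.

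On timing of entry, footnote 1 to Table 3 states: "Screening visit may occur on the same day as the Day 1 visit". Sections 3 and 7.1 allow screening to take place up to 28 days before Day 1.

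**The concern.** Two current sections set a safety rule for the same people and disagree on when it starts and when it ends. The cross-reference adds to the risk: a site applying the inclusion criterion is sent to Section 7.2.3 for the description of contraception, and there it finds the shorter period.

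Two things are at stake. The first is eligibility. The criterion is about what the subject agrees to, so a male who was told of, and agreed to, only the 28-day period has not given the agreement that Section 4.1.2 asks for. The second is protection against partner pregnancy after treatment. Scheduled follow-up ends 4 weeks after the last dose, so no planned visit remains at which a misunderstanding about the later weeks would come to light. Section 7.2.3.2 asks for information on partner pregnancies that arise while the subject is enrolled, so the period in dispute falls largely outside planned contact.

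**Working it through.** The plan states no calculated figure on this point, so the check is a comparison of the two sections plus one subtraction.

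| | Section 4.1.2 | Section 7.2.3.1 |
|---|---|---|
| Who | Males with a female partner of childbearing potential | The same males |
| Start | 2 weeks before first dose | During the study; 14 days before first dose for abstinence only |
| End | 3 months after last dose | 28 days after last dose |

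**Gap at the end.** The protocol does not convert months to days. I use the month length in SAP Section 2.1.1, which is given there for reporting durations: 365.25 / 12 = 30.4375 days.

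- 3 × 30.4375 = 91.3 days
- 91.3 − 28 = 63.3, or about 63 days

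If calendar months are used instead, three consecutive months run from 89 days (28 + 31 + 30) to 92 days (31 + 31 + 30). The gap is then 61 to 64 days (89 − 28 and 92 − 28), so the choice of convention hardly matters.

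**Gap at the start.** 2 × 7 = 14 days. Section 4.1.2 applies it whatever the method; Section 7.2.3.1 applies it to one method.

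**Is it confined to males?** For females, Section 4.1.2 gives 28 days after the last dose and Section 7.2.3.1 gives "during the study until 28 days following the last dose of study treatment". These agree, so the mismatch concerns the male rule only.

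**Is it an artefact?** Both sections are current protocol text. The part of the Amendment 01 change log that can be read (Appendix 2) lists no change to either section on this point. The broken sentence in Section 7.2.3.1 loses its ending but not its duration.

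**Can both be met?** Yes. Day 28 after the last dose falls before day 91, and a period that begins 2 weeks before the first dose covers the study period. A male who follows Section 4.1.2 therefore also satisfies Section 7.2.3.1. The reverse does not hold.

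**How many subjects?** Section 4.1.1 caps enrolment at 12, and Section 4.1.2 admits ages from 1 year to under 18. The documents do not say how many are males with such a partner, so the range is 0 to at most 12, and probably near the low end given the ages admitted.

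**The case against.** The best defence is that Section 4.1.2 is the gate every site must apply, that it states its own period in full, and that its reference to Section 7.2.3 can be read as covering methods only. On that reading the longer period governs and the conflict is nominal. This is a fair reading of the cross-reference, but it does not settle the matter: Section 7.2.3.1 does more than list methods. It states a duration for the same males, and nothing says which section prevails.

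Several stronger readings are tempting, and the documents do not support them.

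- A reader might infer that the rules are incompatible. They are not, because one period lies inside the other.
- A reader might infer that same-day screening makes the 2-week lead-in unattainable. Screening on Day 1 is optional, and up to 28 days is allowed. A male screened on Day 1 might already have been using contraception, for instance during TRA115450, whose requirements are not visible here. All that follows is that the lead-in cannot be started prospectively at a Day 1 screening.
- A reader might infer that every sexually active male is affected. Both sections limit the rule to males with a female partner of childbearing potential.
- A reader might infer that a male who stops at 28 days was enrolled in breach of the criteria. If he had agreed to the longer period at entry, he met the criterion and later departed from his agreement. The eligibility problem arises only where the agreement itself was limited to the shorter period.
- A reader might infer that families are given the wrong period in the consent or assent forms. Those pages are not available and may already state one rule.

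**Conclusion.** The inconsistency is real and should be corrected. The same males are given two end points about 63 days apart (61 to 64 on calendar months), and a 14-day lead-in that is general in one section and tied to a single method in the other. The conclusion rests on the current text of Sections 4.1.2 and 7.2.3.1; the only assumption is the month length, and it makes little difference.

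Its reach is small. It concerns a subset, possibly empty, of at most 12 subjects. It has no bearing on the sample size, the endpoints or any analysis; Section 9.1 plans no hypothesis tests. It is a drafting fault in a safety instruction, worth correcting because the section that sites are referred to carries the shorter period and because planned contact ends at about the point where the two periods diverge. The documents do not show which period was intended, and this review takes no view on that.

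**What to change.** Reconcile Sections 4.1.2 and 7.2.3.1 so that the start and the end of the male contraception period are the same in both, or state the period once and have the other section refer to it. The sponsor decides which period applies. In the same change:

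- say how any lead-in applies to a male whose screening falls on Day 1, as footnote 1 to Table 3 permits;
- make clear whether the period attached to the abstinence method follows the general rule or is separate from it;
- check that the consent and assent text, not visible here, gives the same period, and change it only if it does not.

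The cost is about one sentence of protocol clarification and a check of the subject-facing documents. Nothing in the SAP needs to change.

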#### 4.1.3. Exclusion Criteria

Deviations from exclusion criteria are not allowed because they can potentially jeopardize the scientific integrity of the study, regulatory acceptability or subject safety. Therefore, adherence to the criteria as specified in the protocol is essential.

Subjects meeting any of the following criteria must not be enrolled in the study:

- 1. Subjects with any clinically relevant abnormality, other than ITP, identified on the screening examination or any other medical condition or circumstance, which in the opinion of the investigator makes the subject unsuitable for participation in the study or suggests another primary diagnosis (e.g. Thrombocytopenia is secondary to another disease).
- 2. Any subject considered to be a child in care, defined as one who has been placed under the control or protection of an agency, organization, institution or entity by the courts, the government or a government body, acting in accordance with powers conferred on them by law or regulation. This can include a child cared for by foster parents or living in a care home or institution, provided that the arrangement falls within the definition above. The definition of a child in care does not include a child who is adopted or who has an appointed legal guardian.
- 3. Subjects who have a known immediate or delayed hypersensitivity reaction or idiosyncrasy to drugs chemically related to eltrombopag or excipients that contraindicates their participation.
- 4. Any serious and/or unstable pre-existing medical, psychiatric disorder, or other conditions that could interfere with the subject's safety or compliance to the study procedures.

# 4.2. Permanent Discontinuation from Study Treatment and Subject Completion Criteria

## 4.2.1. Permanent Discontinuation from Study Treatment

Study treatment must be permanently discontinued for any of the following reasons:

- The subject is pregnant.
- The subject is significantly non-compliant with the requirements of the protocol.
- The subject has an adverse experience that would, in the investigator's judgment, make continued participation in the study an unacceptable risk.
- The subject has a thrombotic event, unless in the opinion of the investigator interruption of eltrombopag would lead to a risk of bleeding that would outweigh the risk of thrombosis.
- The subject meets stopping criteria for liver chemistry defined in Section 5.8.1.
- At the request of the subject or proxy

In addition study treatment may be permanently discontinued for any of the following reasons:

TRA117366

- Due to deviation(s) from the protocol
- At the investigator's discretion
- The subject is lost to follow-up
- The study is closed or terminated.

Study treatment will be discontinued within 3 months for the following reasons, and subject will be considered to have completed the study per Section 4.2.2:

- The subject reaches 18 years of age.
- The subject is in treatment phase when local regulatory approval is received for eltrombopag for the treatment of pediatric chronic ITP.

The primary reason study treatment was permanently discontinued must be documented in the subject's medical records and CRF.

If the subject (or guardian) withdrawals consent, the Investigator must document the reason for withdrawal of consent in the CRF if specified by the subject or guardian.

If the subject voluntarily discontinues from treatment due to toxicity, 'adverse event' will be recorded as the primary reason for permanently discontinuation on the CRF rather than subject decision.

Once a subject has been permanently discontinued from study treatment, retreatment with study treatment will not be allowed.

All subjects who discontinue from study treatment will have safety assessments at the time of discontinuation and will have follow-up visits at 1, 2, 3, and 4 weeks after the final dose of study treatment, as specified in Time and Events Table, Table 3.

